### 4.3.3 Exploratory efficacy endpoints (Part A)

- Mean change from baseline in QOL, as assessed by the change in the five level EuroQol – five dimensions questionnaire (EQ-5D-5L) scores at the treatment assessment endpoint
- Mean change from baseline in QOL, as assessed by the change in the 12-Item Short Form Survey (SF-12®) at the end of treatment assessment endpoint
- Proportion of patients with  $\geq 12$  g/dL Hgb at treatment assessment endpoint
- Incidence of thromboembolic events after the first 5 weeks of study drug administration
- Median time to normalization of bilirubin
- Median time to normalization of LDH
- Median time to normalization of haptoglobin
- Median time to Hgb of  $\geq 12$  g/dL
- Proportion of patients normalizing haptoglobin at treatment assessment endpoint

- Proportion of patients normalizing bilirubin at treatment assessment endpoint
- Proportion of patients with abnormal LDH at baseline who normalize LDH at treatment assessment endpoint
- Patient's Global Impression of Change (PGIC) to assess the patient's perception of changes in CAgD disease burden at EOT
- Patient's Global Impression of [Fatigue] Severity (PGIS) to assess the patient's perception of changes in fatigue at EOT
- Incidence of disabling circulatory symptoms at treatment assessment endpoint
- Total healthcare resource utilization at EOT

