### 5.1 INCLUSION CRITERIA

All patients must meet all the following inclusion criteria to be enrolled:

- I 01. Adult male and female patients  $\geq 18$  years of age at Screening.
- I 02. Body weight of  $\geq 39$  kg at Screening.
- I 03. Confirmed diagnosis of primary CAgD based on the following criteria:
  - a) Chronic hemolysis
  - b) Polyspecific direct antiglobulin test (DAT) positive
  - c) Monospecific DAT strongly positive for C3d
  - d) Cold agglutinin titer  $\geq 64$  at  $4^{\circ}\text{C}$
  - e) IgG DAT  $\leq 1+$ , and
  - f) No overt malignant disease
- I 04. Hemoglobin level  $\leq 10.0$  g/dL.
- I 05. Bilirubin level above the normal reference range, including patients with Gilbert's Syndrome.
- I 06. Ferritin levels above the lower limit of normal. Concurrent treatment with iron supplementation is permitted if the patient has been on a stable dose during the previous 4 weeks.
- I 07. Presence of one or more of the following CAgD-related signs or symptoms within 3 months of Screening:
  - a) Symptomatic anemia defined as:
    - i. Fatigue
    - ii. Weakness
    - iii. Shortness of breath
    - iv. Palpitations, fast heart beat
    - v. Light headedness and/or
    - vi. Chest pain
  - b) Acrocyanosis
  - c) Raynaud's syndrome

- d) Hemoglobinuria
  - e) Disabling circulatory symptoms, and/or
  - f) Major adverse vascular event (including thrombosis)
- I 08. Bone marrow biopsy within 6 months of Screening with no overt evidence of lymphoproliferative disease or other hematological malignancy. An additional bone marrow biopsy will be required if the prior bone marrow is deemed unsuitable for analysis by the Sponsor.
- I 09. Documented vaccinations against encapsulated bacterial pathogens (*Neisseria meningitidis*, including serogroup B *meningococcus*, *Haemophilus influenzae*, where available, and *Streptococcus pneumoniae*) within 5 years of enrollment or as specified in [Section 6.1.1.1](#).
- I 10. Patients must be willing to receive transfusions if they meet the eligibility criteria during the study treatment period. Patients who do not have a recent history of transfusion due to patient refusal or patient decision should not be enrolled if they do not agree to receive blood transfusions as needed.
- I 11. Adequate IV access.

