		
 • Incidence of hemolytic breakthrough (rapid fall in Hgb \geq2 g/dL associated with an increase in LDH/bilirubin and/or decrease in haptoglobin since the last scheduled visit) through the EOT at Week 26 • Incidence of infections of \geq Grade 3 severity (ie, requiring intravenous [IV] antibiotics) • Incidence of thromboembolic events
Tertiary/exploratory	
 • To assess the effect of BIVV009 on other quality of life (QOL) measures in patients with primary CAD • To assess the effect of BIVV009 on other laboratory parameters in patients with primary CAD • Pharmacokinetics of BIVV009 • Pharmacodynamics of BIVV009 	
 • Mean change from baseline in QOL, as assessed by the change in the five level EuroQol – five dimensions questionnaire (EQ-5D-5L) scores at the treatment assessment timepoint • Mean change from baseline in QOL, as assessed by the change in the 12-item short form survey (SF-12®) at the end of treatment assessment timepoint • Proportion of patients with Hgb level of \geq12 g/dL at the treatment assessment timepoint • Incidence of thromboembolic events after the first 5 weeks of study drug administration • Median time to normalization of bilirubin • Median time to normalization of LDH • Median time to normalization of haptoglobin • Median time to obtain Hgb level of \geq12 g/dL • Proportion of patients normalizing haptoglobin at the treatment assessment timepoint • Proportion of patients normalizing bilirubin at the treatment assessment timepoint • Proportion of patients with abnormal LDH at baseline who normalize LDH at treatment assessment timepoint • Patient’s Global Impression of Change (PGIC) to assess patient’s perception of changes in CAgD disease burden at EOT • Patient’s Global Impression of [Fatigue] severity (PGIS) to assess the patient’s perception of changes in fatigue at EOT • Incidence of disabling circulatory symptoms at treatment assessment timepoint • Total healthcare resource utilization at EOT • Plasma concentrations of BIVV009 • PK parameters: Appropriate exposure parameters (Cmax, AUC) will be derived using a population PK approach • Plasma concentrations of BIVV009 • PK parameters: Appropriate exposure parameters (Cmax, AUC) will be derived using a population PK approach

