 - Cerebral infarction, occlusion, and stenosis of cerebral and precerebral arteries
 - Vascular syndromes of brain in cerebrovascular diseases, transient cerebral ischemic attacks, and related syndromes
- Any arterial events
 - Myocardial infarction
 - Mesenteric arterial thrombosis
 - Other arterial embolism and thrombosis

Medical review of medical history and AEs will ascertain thromboembolic events for analysis.

Normalization of Bilirubin

The normalization of bilirubin is defined as total bilirubin \leq upper limit of normal (ULN) (specified by the central lab).

Normalization of LDH

The normalization of LDH is defined as LDH value \leq ULN (specified by the central lab).

Normalization of Haptoglobin

The normalization of haptoglobin is defined as haptoglobin above the level of detection.

Normalization of Hemoglobin

The normalization of hemoglobin is defined as hemoglobin ≥ 12 g/dL. Hemoglobin ≥ 11 g/dL will also be investigated.

Hemolytic Breakthrough

Hemolytic breakthrough at any visit is defined as

- A decrease of 2 g/dL or more in Hgb from the last scheduled visit, and
- One of the followings:
 - An increase of LDH from the last scheduled visit,

- An increase of bilirubin from the last scheduled visit,
- A decrease in haptoglobin from the last scheduled visit.

Protocol Prohibited CAD Medications

The following concomitant medications are prohibited during the study treatment period in Part A:

- Rituximab alone or as part of combination therapy
- Cytotoxic drugs (such as fludarabine, bendamustine, ibrutinib, cyclophosphamide)
- Other investigational drugs

The efficacy endpoint (estimand) accounting for protocol prohibited CAD medication(s) use will be based on the eCRF questionnaire “Did the subject receive any prohibited medications since the last visit?” at post-baseline visits. The medical review for the list of prohibited medications will be reconciled with the eCRF questionnaire.

Pooling Sites for Analysis

Data from all investigational sites will be pooled for the analysis, unless specified otherwise.

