4.4.2 Supportive secondary endpoint(s)

Additional analyses for hemoglobin and bilirubin

To further understand the clinical effect of BIVV009 in increasing hemoglobin level compared with placebo, the number of subjects with an increase of hemoglobin level from baseline ≥ 1 g/dL, ≥ 1.5 g/dL, ≥ 2 g/dL and ≥ 3 g/dL at TAT will be reported for BIVV009 and for placebo.

Mean Change from Baseline in Bilirubin by visit (including TAT)

Total bilirubin will be summarized by-visit, including change from baseline, using the Full Analysis Set, with subjects with Gilbert's syndrome or unknown Gilbert's test result excluded.

If the number of subjects with unknown Gilbert's syndrome status is greater than 2, additional sensitivity analysis will be performed to include such subjects (unknown Gilbert's syndrome).

Mean Change from Baseline in Lactate Dehydrogenase (LDH) by visit (including TAT)

LDH will be summarized by-visit, including change from baseline, using the Full Analysis Set.

Additional descriptive analyses will be performed for LDH isoforms.

Incidence of Solicited Symptomatic Anemia

- Incidence of solicited symptomatic anemia will be summarized by visit descriptively using the FAS. The summaries will be based on observed data only and missing grades will not be imputed.

- An improvement in each anemia symptom is defined as at least 1 grade reduction from baseline; whereas worsening is defined as at least 1 grade increase from baseline. The percentage of improved and worsened subjects for each symptom will be presented by visit; this percentage is calculated based on the number of subjects with no missing grade at both baseline and each post-baseline visit.
- The improvement (worsening) in all anemia symptoms is defined as at least 1 grade reduction (increase) in at least 1 symptom, and no worsening (improvement) in other remaining symptoms. The proportion of subjects improved and worsened in all anemia symptoms will be summarized by visit.

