4.5.1 Definition of endpoint(s)

Continuous Endpoints

The continuous endpoints include:

- Mean change from baseline in QOL, as assessed by the change in the five level EQ-5D-5L scores at the treatment assessment timepoint (TAT) and by visit
- Mean change from baseline in QOL, as assessed by the change in the 12-item short form survey (SF-12®) at the end of treatment assessment endpoint and by visit
- Mean change from baseline in hemolytic parameters (Hgb, total bilirubin, LDH, haptoglobin, and absolute reticulocyte) by visit
- Mean change from baseline in FACIT-F by visit

Response (Categorical) Endpoints

The response endpoints include (order different from protocol and not reflecting importance):

- Incidence of thromboembolic events after the first 5 weeks of study drug administration
- Incidence of CAD-related symptoms at last scheduled visit of Part A
- Total healthcare resource utilization at EOT (Part A)
- Proportion of subjects normalizing Hgb (≥ 12 g/dL) at TAT and by visit
- Proportion of subjects achieving 1.5 g/dL increase in Hgb at TAT and by visit
- Proportion of subjects normalizing bilirubin at TAT and by visit

- Proportion of subjects normalizing LDH at TAT and by visit (Proportion of subjects with $LDH \leq 1.5 \times ULN$ at TAT will also be reported)
- Proportion of subjects normalizing haptoglobin at TAT and by visit
- PGIC and change from baseline in PGIS to assess subject's perception of changes in CAgD disease burden at last scheduled visit of Part A

Time-to-Event Endpoints

Time-to-event endpoints include:

- Time to first transfusion after the first 5 weeks of study drug administration from the first dose of study drug
- Time to first transfusion (including the first 5 weeks of study drug administration) from the first dose of study drug
- For subjects who do not receive any transfusion, their time-to-event will be censored at the study day of the last scheduled visit in Part A.
- Time to first normalization of bilirubin from the first dose of study drug
- Time to first normalization of LDH from the first dose of study drug
- Time to first normalization of haptoglobin from the first dose of study drug
- Time to first normalization of Hgb level (≥ 12 g/dL)
- Time to first achieving 1.5 g/dL increase in Hgb level

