4.5.2 Main analytical approach

Continuous Endpoints

The continuous endpoints will be summarized by visit and treatment arm using descriptive statistics for the FAS according to [Section 4.1](#).

For EQ-5D index score and SF-12 component scores (physical component score and mental component score), an ANCOVA (Analysis of Covariance) model will be implemented, where treatment arm is the fixed effect, and the baseline score is the covariate; a 95% confidence interval for the treatment effect difference and the corresponding p-value will be generated. The treatment difference and 95% CI will be estimated by ANOVA with treatment and baseline value as independent variables.

Response (Categorical) Endpoints

The categorical endpoints will be summarized descriptively by visit for the FAS according to [Section 4.1](#) with the exception of total healthcare resource utilization at EOT (Part A), which will be presented in a listing.

All thromboembolic events reported (in Adverse Events) will be reviewed and determined by internal medical staff along with investigators. In case that there are discrepancies between the medical review and investigators' assessment, separate analyses will be carried out for both sets of events. Date of event occurrences will be verified. The detailed listing for all events will be provided including date (study day) of onset, verbatim terms of the event, and the flag for whether the event occurred after the first 5 weeks of study drug administration. Incidence of thromboembolic events will be calculated as the total number of thromboembolic events after the first 5 weeks of study drug administration divided by the total subject-years of time for observation (ie, time from Week 5 through Week 26 or EOT visit for subjects who discontinue early). All events from Week 5 through Week 26 or EOT visit for subjects who discontinue early will be included. A 95% exact CI will be provided.

Time-to-Event Endpoints

All time-to-event endpoints will be analyzed by treatment group for the FAS using the Kaplan-Meier method outlined in [Section 4.1](#). For subjects who receive transfusions after Week 5 infusion, the time to normalization will be censored at the study day of the transfusion visit. For subjects who do not experience normalization, the data will be censored at the study day of the last assessment in Part A.

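### SAP 4.5.1 drops the abnormal-baseline condition for LDH normalization, and SAP 4.1 sets none for LDH or haptoglobin, so patients already normal at Day 0 can be counted as normalizing

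*SAP*

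**What the plan says.** **LDH proportion, restricted.** Protocol 4.3.3 lists "Proportion of patients with abnormal LDH at baseline who normalize LDH at treatment assessment endpoint". SAP 1.2, Table 2, repeats it: "Proportion of patients with abnormal LDH at baseline who normalize LDH at treatment assessment timepoint".

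**LDH proportion, unrestricted.** SAP 4.5.1 lists "Proportion of subjects normalizing LDH at TAT and by visit". SAP 4.5.2 then says: "The categorical endpoints will be summarized descriptively by visit for the FAS". Time to first normalization of LDH, haptoglobin and bilirubin is also analyzed in the FAS, by Kaplan-Meier.

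**Definitions.** SAP 4.1 states "The normalization of LDH is defined as LDH value" at or below the upper limit of normal (ULN). Haptoglobin normalization is any value above the level of detection. Neither definition mentions the baseline value.

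**Bilirubin.** Inclusion criterion I 05 reads "Bilirubin level above the normal reference range, including patients with" Gilbert's Syndrome. SAP 4.4.2 removes these patients, and those of unknown status ("or unknown Gilbert's test result excluded"), from the change-from-baseline summary. SAP 4.5.1 lists "Proportion of subjects normalizing bilirubin at TAT and by visit" with no such exclusion, and also lists bilirubin among the parameters whose mean change is summarized by visit.

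**The concern.** Normalizing means moving from abnormal to normal. A level-only definition applied to everyone also counts patients who had nothing to normalize. Bilirubin above normal is an entry criterion, but the protocol sets no LDH or haptoglobin threshold for entry, so some patients may be normal on either at Day 0. The abnormal-baseline wording in Protocol 4.3.3 and SAP Table 2 suggests the authors expected this for LDH.

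At stake is the meaning of the reported proportions and times. Placebo patients whose LDH never changed could appear as having normalized, which would on average understate the contrast with drug. The LDH result would also not be the endpoint that the protocol names. For bilirubin, results in the same report could rest on different populations without a stated reason.

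**Working it through.** **Step 1: which text governs?**
- Protocol section 7 gives the SAP precedence where the two differ, so the protocol wording does not settle the matter.
- Within the SAP, Table 2 carries the restriction and 4.5.1 does not. SAP 4.5 says the exploratory analyses are outlined in its subsections, so a programmer would work from 4.5.1 and 4.5.2.
- SAP 4.5.1 notes that its order differs from the protocol, but mentions no change of population. Appendix 2 (Table 13) records no change.
- SAP 4.5 points to an Observed Estimand in 1.2.1. That section defines none by that name, so it does not resolve the population.

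**Step 2: effect on the proportion.** The plan gives no figure for these endpoints. Its 87% power (Protocol 7.10) concerns the primary endpoint; it reproduces as 87.5% with Fisher's exact test and 20 per group, and has no bearing here.

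Let q be the share normal at baseline, and pT and pC the normalization rates on drug and placebo among patients abnormal at baseline. All three are assumptions. If baseline-normal patients stay normal, each arm's reported rate is q + (1−q)p, and the difference is (1−q)(pT − pC). With pT = 70% and pC = 0%:

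| q | Drug | Placebo | Difference |
|---|---|---|---|
| 10% | 0.10 + 0.90×0.70 = 73% | 10% | 63 points |
| 30% | 0.30 + 0.70×0.70 = 79% | 30% | 49 points |
| 50% | 0.50 + 0.50×0.70 = 85% | 50% | 35 points |

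With 70% vs 10% the factor is the same: 60 points becomes 54, 42 and 30.

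**Step 3: relax the assumption that they stay normal.** Take q = 20% and 70% vs 10%. Suppose every baseline-normal drug patient stays normal but 30% of those on placebo become abnormal.
- Drug: 0.20 + 0.80×0.70 = 76%.
- Placebo: 0.20×0.70 + 0.80×0.10 = 22%.
- The difference is 54 points, against 0.80×60 = 48 if all stay normal.

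**Step 4: chance imbalance.** With 20 per arm (Protocol 7.10), the SD of the between-arm difference in q is √(2q(1−q)/20): 9.5 points at q = 10%, 14.5 at 30% and 15.8 at 50%. With 70% vs 10%:
- q = 10% on drug and 30% on placebo: 73% − 37% = 36 points.
- q = 30% on drug and 10% on placebo: 79% − 19% = 60 points.
- Balanced at 20%: 48 points.

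**Step 5: time to normalization.** A baseline-normal patient still normal at Day 7 has an event at the Week 1 visit on either arm. These patients alone put the median at that visit only once q reaches about 50%.

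**Step 6: bilirubin.** Let g be the share with Gilbert's syndrome and suppose none ever reaches the ULN. The difference is then (1−g)(pT − pC): 60 points becomes 57 at g = 5% and 54 at g = 10%. The documents give neither g nor that supposition.

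**The case against.** The strongest reply is that this is a drafting slip. Table 2 of the same SAP keeps the LDH restriction, 4.5.1 presents itself as a reordering of the protocol's list, and no change is logged. That is fair: the SAP contradicts itself on the LDH proportion, and whole-FAS scoring is one of two readings. The slip still needs correcting, because the less suitable reading sits where the analysis is specified.

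The other points on this side largely stand:
- For haptoglobin, and for time to normalization of any parameter, neither document states a baseline restriction. This is a gap, not a contradiction.
- Each visit is scored on that visit's value. Protocol 2.2 describes disease activity as fluctuating, so a patient normal at Day 0 does not automatically count at every visit.
- Percentages use non-missing data (SAP 4.1), so the denominator is not strictly the whole FAS.
- The protocol attaches the Gilbert's exclusion only to mean change in bilirubin (4.3.2). Extending it to normalization is a proposal, not the repair of a departure.
- The 4.5.1 by-visit bilirubin change may be the 4.4.2 summary listed again, not a second table.

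A reader might infer that bilirubin has the same already-normal problem, or that Gilbert's patients are counted as failures. I 05 largely rules out the former; only a fall between screening and Day 0 could produce it. No rule does the latter: these patients are scored on their measured level, and are censored in the Kaplan-Meier analysis if they do not normalize.

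**Conclusion.** The concern holds for LDH as an unrecorded inconsistency between SAP 4.5.1/4.5.2 and both Protocol 4.3.3 and SAP Table 2. It holds for haptoglobin and for time to normalization as a missing baseline condition. Under the text of 4.5.1, patients already normal at Day 0 can count as normalizing and as early events on either arm.

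The expected attenuation is the factor (1−q) if those patients stay normal and q is equal between arms. The documents supply neither q nor the response rates, so the point figures are illustrations only. A reader might infer that the effect is always diluted, or that the median times cannot be interpreted. The documents support neither: imbalance at 20 per arm can move the contrast either way, and the median is dominated by these patients only near q = 50%, a share for which the documents give no evidence.

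The consequence is limited. These endpoints are exploratory, summarized descriptively, and outside the testing sequence in SAP 4.6, which covers the primary endpoint, hemoglobin and FACIT-F. The correction is worth making because it restores the protocol's own LDH endpoint at little cost.

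**What to change.** In SAP 4.5.1 and 4.5.2:
- Restrict LDH normalization to FAS patients with baseline LDH above the ULN. For the proportion this matches Protocol 4.3.3 and Table 2; apply the same subset to time to first normalization.
- Apply the equivalent rule to haptoglobin: patients whose baseline value is below the level of detection.
- Show the denominator for each arm.
- Present bilirubin normalization both in the full FAS and with Gilbert's and unknown-status patients excluded. State that the 4.5.1 by-visit bilirubin change uses the same population as 4.4.2.

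The cost is SAP wording and one subset flag per parameter. LDH, haptoglobin and bilirubin are in the chemistry panel taken at Day 0, and the UGT1A1 test is done at screening, so no new data are needed. The downside is smaller denominators: with 20 per arm, 20×0.90 = 18 at q = 10% and 20×0.70 = 14 at q = 30%.

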4.5.2 Main analytical approach

Continuous Endpoints

The continuous endpoints will be summarized by visit and treatment arm using descriptive statistics for the FAS according to [Section 4.1](#).

For EQ-5D index score and SF-12 component scores (physical component score and mental component score), an ANCOVA (Analysis of Covariance) model will be implemented, where treatment arm is the fixed effect, and the baseline score is the covariate; a 95% confidence interval for the treatment effect difference and the corresponding p-value will be generated. The treatment difference and 95% CI will be estimated by ANOVA with treatment and baseline value as independent variables.

Response (Categorical) Endpoints

The categorical endpoints will be summarized descriptively by visit for the FAS according to [Section 4.1](#) with the exception of total healthcare resource utilization at EOT (Part A), which will be presented in a listing.

All thromboembolic events reported (in Adverse Events) will be reviewed and determined by internal medical staff along with investigators. In case that there are discrepancies between the medical review and investigators' assessment, separate analyses will be carried out for both sets of events. Date of event occurrences will be verified. The detailed listing for all events will be provided including date (study day) of onset, verbatim terms of the event, and the flag for whether the event occurred after the first 5 weeks of study drug administration. Incidence of thromboembolic events will be calculated as the total number of thromboembolic events after the first 5 weeks of study drug administration divided by the total subject-years of time for observation (ie, time from Week 5 through Week 26 or EOT visit for subjects who discontinue early). All events from Week 5 through Week 26 or EOT visit for subjects who discontinue early will be included. A 95% exact CI will be provided.

Time-to-Event Endpoints

All time-to-event endpoints will be analyzed by treatment group for the FAS using the Kaplan-Meier method outlined in [Section 4.1](#). For subjects who receive transfusions after Week 5 infusion, the time to normalization will be censored at the study day of the transfusion visit. For subjects who do not experience normalization, the data will be censored at the study day of the last assessment in Part A.

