**Table 2 - Responder definition**

A patient will be considered a responder in Part A if:

- Hgb increases  $\geq 1.5$  g/dL from baseline (defined as the last Hgb value before administration of the first dose of study drug) at treatment assessment endpoint (defined as mean value from Weeks 23, 25, and 26) and
- The patient did not receive a blood transfusion from Week 5 through Week 26 (EOT), and
- The patient did not receive treatment for CAgD beyond what is permitted per protocol from Week 5 through Week 26 (EOT)

A list of excluded concomitant medications, as well as allowed concomitant medications with restrictions, is provided in [Section 6.2.6](#). Beyond the permitted concomitant medications, study drug, and transfusions, patients may receive no other therapies for the treatment of CAgD while enrolled in this study; patients requiring other treatment for their CAgD in Part A will be withdrawn from the study and counted as non-responders. These patients will not be eligible to participate in Part B.

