4.1 GENERAL CONSIDERATIONS

Safety, efficacy, and PK/PD data will be summarized using standard summary statistics for continuous, categorical, and event-time data. Data will be summarized for the populations defined. All statistical hypothesis testing will be performed at the 2-sided, 5% significance level, unless specified otherwise. All p-values will be presented to 3 decimal places; p-values less than 0.001 will be presented as “<0.001,” and p-values greater the 0.999 will be presented as “>0.999.”

Unless otherwise specified, analyses will be performed by intervention group (and overall for baseline and demographics characteristics).

Continuous variables will be summarized using descriptive statistics including the number of non-missing values (n), mean, standard deviation (SD), median, minimum, and maximum. Where specified in the table shells, the 25th and 75th percentiles will also be provided. Means, medians, and the 25th and 75th percentiles will be presented to one decimal place beyond that with which the data were captured. SDs will be presented to two decimal places beyond that with which the data were captured. Minimum and maximum will be displayed to the same number of decimal places as that with which the data were captured.

Categorical variables will be summarized by counts and percentages. All percentages will be rounded to one decimal place. The percentage will be suppressed when the count is zero. Unless specified otherwise, the denominator for all percentages will be the number of non-missing data for a given summarization.

Time-to-event variables will be summarized using Kaplan-Meier estimate over time, along with median time to event and probability of an event at specific time points. Partial dates will not be imputed, hence considered unknown. In general, for subjects who do not experience the event, they will be censored at the study day of last assessment within Part A.

Part A Study Treatment Period

The Part A study treatment period starts at the date of first dose of study drug and ends at the date of Week 26 Visit if the subject completes Part A study treatment, or at the date of Early Termination (ET)/Safety Follow-up Visit if the subject discontinues the study treatment prior to Week 25.

Treatment Assessment Timepoint (TAT)

The value of an assessment (eg, Hgb) at the treatment assessment timepoint is defined as the average of the values from Week 23, 25, and 26 visits. In the case of any missing value at any of

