4.3 PRIMARY ENDPOINT(S) ANALYSIS

4.3.1 Definition of endpoint(s)

The primary endpoint is the responder rate, defined in [Section 1.2](#), and is a composite endpoint of the following components:

1. Free of post-baseline transfusion within the range of Week 5 and Week 26 visit dates;
2. Change from baseline in Hgb at treatment assessment timepoint is ≥ 1.5 g/dL,
3. Receive no protocol prohibited medications (defined in [Section 4.1](#)) within the range of Week 5 and Week 26 visit dates

Components 1 and 3 will be determined by the corresponding questions in eCRF at all visits (from Week 5 through Week 26) in Part A.

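### Censoring time to normalization at a post-Week-5 transfusion makes Kaplan-Meier overstate the proportion normalizing and shorten the median (exploratory endpoints only)

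*SAP*

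**What the plan says.** Part A SAP 4.5.1 lists time to first normalization of bilirubin, LDH, haptoglobin and hemoglobin (for example "Time to first normalization of bilirubin from the first dose of study drug"), and time to a first 1.5 g/dL rise in hemoglobin. Protocol 4.3.3 states the normalization endpoints as median times.

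On method, SAP 4.5.2 says "All time-to-event endpoints will be analyzed by treatment group for the FAS using the Kaplan-Meier method", and SAP 4.1 promises Kaplan-Meier estimates "along with median time to event and probability of an event at specific time points". Two censoring rules follow in 4.5.2:

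- Transfused patients: "For subjects who receive transfusions after Week 5 infusion", "the time to normalization will be censored at the study day of the transfusion visit".
- The others: "For subjects who do not experience normalization, the data will be censored at the study day of the last assessment in Part A".

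Elsewhere a transfusion in the same period is a failure. Protocol Table 2 requires of a responder that "The patient did not receive a blood transfusion from Week 5 through Week 26 (EOT), and" the remaining criteria are also met. SAP 4.3.1 repeats the component: "Free of post-baseline transfusion within the range of Week 5 and Week 26 visit dates". Protocol Table 1 sets the trigger for transfusion at hemoglobin below 9 g/dL with symptoms or below 7 g/dL without. SAP 4.1 sets hemoglobin normalization at 12 g/dL or more.

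SAP 4.5 places the exploratory endpoints under an Observed Estimand said to be defined in Section 1.2.1. No estimand of that name appears there.

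**The concern.** Kaplan-Meier treats a censored patient as having the same later prospects as those still being followed. Here the event that censors is triggered by hemoglobin at least 3 g/dL below the normalization threshold. For hemoglobin the dependence is direct. For bilirubin, LDH and haptoglobin it is indirect: the anemia that leads to transfusion comes from the hemolysis that these markers measure.

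The two rules also rank failures oddly. A patient who never normalizes and is never transfused stays in the denominator to the last Part A assessment. A patient who does worse and needs blood leaves it.

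At stake are the reported normalization probabilities and the median times, which are the summaries that the protocol names. The probabilities come out too high and the medians too early.

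**Working it through.** The plan gives no figure for these endpoints, so there is nothing of its own to reproduce. From the documents come the estimator, the censoring rules and 20 patients per group (Protocol 7.10). Transfusion rates, normalization rates and timing are assumptions. Below, the true proportion means the share who normalize in Part A before any post-Week-5 transfusion.

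**1. One arm of 20, by hand.** Assume 8 patients normalize, at Weeks 3, 5, 9, 11, 13, 15, 17 and 21. Assume *k* others are transfused at evenly spaced times from Week 6 to Week 14, and the rest are followed to Week 26. The true proportion is 8/20 = 40%, with no median.

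For *k* = 2 (Weeks 6 and 14) the numbers at risk at the eight event times are 20, 19, 17, 16, 15, 13, 12 and 11:

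S = (19/20)(18/19) × (16/17)(15/16)(14/15) × (12/13)(11/12)(10/11) = 0.9 × 14/17 × 10/13 = 0.570

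So 1 − S = 43.0%. The same calculation for larger *k*:

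| Transfused | 1 − KM at Week 26, censored | Median, censored | Kept at risk as not normalized |
|---|---|---|---|
| 2 | 43.0% | not reached | 40.0%, not reached |
| 4 | 47.1% | not reached | 40.0%, not reached |
| 6 | 52.8% | Week 21 | 40.0%, not reached |
| 8 | 60.9% | Week 17 | 40.0%, not reached |

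With 6 or 8 transfused, the planned analysis reports a median although fewer than half normalized.

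**2. Normalization spread over Weeks 5 to 26.** Let a fraction *p* normalize and a fraction *q* be transfused and not normalize, both uniformly over the window. After a fraction *u* of the window, 1 − (p + q)u remain at risk and the hazard of normalization is p / [1 − (p + q)u]. Integrating over the window gives

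1 − KM = 1 − (1 − p − q)^(p/(p+q))

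| True p | Transfused q | Calculation | 1 − KM | Excess, points |
|---|---|---|---|---|
| 20% | 10% | 1 − 0.7^0.667 | 21.2% | 1.2 |
| 20% | 30% | 1 − 0.5^0.4 | 24.2% | 4.2 |
| 20% | 50% | 1 − 0.3^0.286 | 29.1% | 9.1 |
| 30% | 50% | 1 − 0.2^0.375 | 45.3% | 15.3 |

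Simulation with 20 per arm, letting normalization start anywhere from Week 0 to Week 5, gives about 21%, 23–24%, 28–29% and 43–45%.

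**3. Early normalization.** The same simulation with normalization confined to Weeks 1 to 9 gives 20.4%, 20.7% and 31.2% for the last three rows, an excess of at most about 1 point. If all normalization occurs by Week 5 the excess is zero, because the rule acts only after the Week 5 infusion.

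**4. Constant independent hazards as a cross-check.** Over T = 21 weeks with hazards *l* (normalization) and *m* (transfusion), cumulative incidence is l/(l + m) × [1 − exp(−(l + m)T)]. With KM at 50% and transfusion probability 10%, this is ln 0.5/(ln 0.5 + ln 0.9) × (1 − 0.5 × 0.9) = 0.868 × 0.55 = 47.7%, a gap of 2.3 points. At 30% transfused it is 42.9%, a gap of 7.1 points. Here the two hazards are independent, yet 1 − KM still exceeds the share who actually normalize. Even with harmless censoring, Kaplan-Meier answers a hypothetical question that the SAP has not posed for these endpoints.

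**The case against.** The best case on the other side has five parts.

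- **Timing.** Protocol 2.2.2 describes an immediate stop to hemolysis and rapid correction of anemia. If BIVV009 patients normalize early, that arm's curve is barely affected. This stands, and the size must be given as a range that includes zero.
- **Rates.** Transfusion rates of 30% to 50% have no source in the documents, and patients enter with no transfusion in the previous 6 months. This stands too. One patient in an arm of 20 is 5 points, so a shift from 20% to 24% is less than one patient.
- **Other summaries.** The SAP also reports proportions normalizing at the treatment assessment timepoint and by visit, time to first transfusion, and transfusion counts by period and arm. These show how much censoring occurred but do not correct the medians.
- **Estimand.** Discarding values after transfusion matches the hypothetical strategy set for the key secondary hemoglobin and FACIT-F analyses. That is a possible defense, but no such estimand is stated for these endpoints, and it would still need censoring unrelated to prognosis.
- **Direction.** A reader might infer that the rule flatters BIVV009. The documents do not support that. If placebo patients are transfused more often, their curve is inflated more and the difference between arms tends to shrink.

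A reader might also infer that transfusions before Week 5, which are not censored, commonly create hemoglobin normalization. From a trigger below 9 g/dL, reaching 12 g/dL needs a rise of more than 3 g/dL, and Protocol 2.2 says that transfused cells are destroyed by the same mechanism. The point matters mainly for the 1.5 g/dL rise. The SAP does not call that endpoint normalization, so the censoring rule may not cover it even after Week 5.

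**Conclusion.** The concern holds in a limited form. Censoring at a post-Week-5 transfusion is informative, so the planned curve overstates the proportion normalizing and the median is too short, or finite when fewer than half normalize.

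The size rests on assumed transfusion rates and normalization timing. It is near zero if normalization is complete by about Week 9. If normalization is spread over Part A, it is about 1 point (20% true, 10% transfused), 3 to 4 points (20% true, 30% transfused), or 8 to 15 points (20% to 30% true, 50% transfused). The last two figures assume that transfused patients do not normalize.

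It would be wrong to read this as a threat to the trial's conclusions. The endpoints are exploratory, no test between arms is planned for them, and the primary and key secondary analyses do not use this rule. It is a cheap improvement, not a necessary correction.

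**What to change.** In Part A SAP 4.5.2, make the main analysis the cumulative incidence of normalization, with transfusion after the Week 5 infusion as a competing event. Equivalently, keep a transfused patient at risk as not normalized to the end of Part A; the two coincide when there is no other censoring. A patient who normalized before the transfusion keeps the event. Take the median and the probabilities at set times from that curve. This matches how the primary endpoint treats transfusion.

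Add two short items:

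- For the hemoglobin endpoints, above all the 1.5 g/dL rise, state that an event shortly after any transfusion is not counted, and fix the interval before unblinding.
- Define the Observed Estimand, or remove the reference to it.

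The cost is SAP wording and a standard procedure, with no new data. The downside is that the estimate no longer describes a setting without transfusion, so the current Kaplan-Meier analysis can stay as supplementary, labeled as hypothetical.
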